**Appendix 6 Medications Known to Cause Prolongation of the QT Interval or Torsades de Pointes**

For the most current list of medications, refer to: <https://crediblemeds.org/> (free registration required).

All medications listed in the table are a known risk of TdP and are prohibited while on study. This list is not considered comprehensive and the Crediblemeds site should be referenced for the most up to date listing.

Class	Medication
Anesthetics	Propofol
	Sevoflurane
Antiarrhythmics	Amiodarone
	Disopyramide
	Dofetilide
	Dronedarone
	Flecainide
	Ibutilide
	Procainamide
	Quinidine
Sotalol	
Other cardiac drugs	Bepidil
Antineoplastic Agent	Oxaliplatin
Antipsychotics	Chlorpromazine
	Haloperidol
	Levomepromazine
	Levosulpiride
	Mesoridazine
	Pimozide
	Sulpiride
	Sultopride
	Thioridazine
Antibacterials	Azithromycin
	Ciprofloxacin
	Erythromycin
	Clarithromycin
	Gatifloxacin
	Grepafoxacin
	Levofloxacin
	Moxifloxacin
	Roxithromycin
	Sparfloxacin

Antidepressants	Citalopram
	Escitalopram
Antifungals	Fluconazole
	Pentamidine
Antimalarials	Chloroquine
	Halofantrine
Opiates	Methadone
	Levomethadyl
Anti-emetics	Cisapride
	Domperidone
	Droperidol
	Ondansetron
Antihistamines	Astemizole
	Terfenadine
Anti-cancer agents	Arsenic trioxide
	Vandetanib
Miscellaneous	<del>Clobutinol</del>
	Anagrelide
	Cilostazol
	Cocaine
	Donepezil
	Ibogaine
	Papaverine
	Probutol
	Terlipressin
	Terodiline

### **Protocol Version 3: AURA-001(b), 1/June/2017**

Protocol AURA-001 [A Phase I/II Open-Label Multicenter Study to Evaluate the Safety and Efficacy of AK-01 as Monotherapy in Patients with Locally Advanced or Metastatic Solid Tumors] has been amended to create Version 3, dated 1/June/2017. The new protocol is indicated by amendment (b) and will be used to conduct the study in place of any preceding version of the protocol.

The overall changes and rationale for the changes made to this protocol are as follows:

#### **3.4. Discussion of Design and Control**

Clarification has been provided to the modified 3+3 statistical design.

#### **Summary of Protocol Changes**

Inclusion/Exclusion Criteria Rationale for the renal inclusion criteria is updated.

## Revised Protocol Sections

Note:	Deletions have been identified by <del>strikethroughs</del> or grayed out for figures. Additions have been identified by the use of underscore .
--------------	---

### 3.4. Discussion of Design and Control

Phase I is a dose escalation study with a modified 3 + 3 design. The 3+3 design is modified to allow expansion of a cohort with 3 additional patients if 1 DLT is observed in 6 patients for a total of 9 patients in the cohort (see Figure 2). The rules-based 3 + 3 method for dose escalation is well-established, safe, and does not require real-time PK or computational modeling. Inpatient dose escalation is permitted to allow each patient to potentially receive a maximum tolerated dose of AK-01 (see Section 3.1.4). In Phase II, preliminary efficacy of AK-01 will be assessed in up to 3 cohorts (BC, SCLC, and/or one other solid tumor of interest). Preclinical evidence indicates AK-01 may be particularly efficacious in these tumor types. Since this is not a comparison study, the use of a placebo control is not applicable.

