### 3.1.4. Inpatient Dose Adjustments

Dose modifications for toxicity are described in [Section 3.3.2](#).

Following Cycle 1, if no DLT-equivalent toxicity is experienced, a given patient’s dose may be maintained or escalated (provided the dose does not exceed the MTD). The decision to dose escalate a patient after Cycle 1 will be recommended by the investigator and discussed with the sponsor’s medical representative. A patient can only be escalated to a dose level at which a

minimum of 3 patients have completed Cycle 1 and which has been deemed acceptable by the SAC. Inpatient AK-01 dose escalation may occur following completion of the patient's current cycle.

Any patient who continues in the study following Cycle 1 will be assessed for toxicity and tolerability throughout their participation. The safety and tolerability of dose escalation in these patients may guide dose decisions for new cohorts.

Following completion of Cycle 1, dosing may continue in 21-day cycles until disease progression if the patient is receiving benefit and is experiencing no severe toxicity in the opinion of the investigator.

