### 7.2. Labels and Tags Used in SAP and/or Outputs

For indication of cohorts, the following labels will be used in the outputs:

- Phase I, where cohorts are defined by the dose assigned: AK-01 25mg BID, AK-01 50mg BID, AK-01 75mg BID, etc.
- Phase II, where cohorts are defined by the tumor type: BC, SCLC, etc. (based on the indications selected)

For indications of time-points, the notation will include cycle and day numbers, e.g. “Cycle 2 Day 8” or “C2D8”.

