### 9.1. General Principles

The IBA internal standard operating procedure "SOP111 Statistical analysis of clinical data" serves as a general guideline on methodology and practical aspects to be considered when carrying out statistical analysis of clinical data. Any data inspection and analyses should take into consideration the principles outlined therein.

Statistical package SAS [4], version 9.4 or higher, will be used for the analysis and for generation of tables, figures and listings (TFL). Statistical package R [5] may be used for creation of specific graphs that will be validated in SAS.

All tables, figures and listings will be presented separately by phase. Further, each table/listing will present the data by cohort, that it by dose cohort in phase I and by tumor type in phase II. The tables related to baseline patient characteristics will include a 'Total' column for phase I patients where appropriate. The efficacy endpoints in phase I will be considered overall (i.e. all dose cohorts combined) and for the MTD cohort only. Efficacy in phase II will be summarized by cohort. The listings will present data by patient. In case the tables and figures summarizing only one subject, the statistic description and visualization would not be useful and the listings will be presented only.

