#### **Relative dose intensity**

Planned dose intensity is the dose by unit of time planned to be given to the patients as per the assigned cohort. Relative dose intensity is defined as Dose intensity/Planned dose intensity.

Cumulative dose, dose intensity and relative dose intensity will be summarized by descriptive statistics by cohort, with respect to an individual duration of treatment exposure as well as by cycle. The relative dose intensity will be summarized as continuous variable as well as by categories (<80%, 80%-120%, >120%).

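### SAP 9.7.1 measures Phase I relative dose intensity against the assigned cohort's dose, so a permitted escalation reads as over-dosing and can mask missed doses

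*Protocol*

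**What the plan says.** Protocol 3.4 gives the purpose of raising the dose within a patient: "Inpatient dose escalation is permitted to allow each patient to potentially receive a maximum tolerated dose of AK-01". (The printed word is evidently meant as intrapatient, since Protocol 3.1.4 describes changing an individual's dose.) Protocol 3.1.4 sets three limits. Escalation comes only after Cycle 1, may not go above the MTD, and may go only to a level at which a "minimum of 3 patients have completed Cycle 1 and which has been deemed acceptable by the SAC". SAP 5.1.1 repeats the permission. Phase II allows no increases (Protocol 3.2, SAP 5.1.2).

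On exposure, SAP 9.7.1 says that "Planned dose intensity is the dose by unit of time planned to be given to the patients as per the assigned cohort" and that "Relative dose intensity is defined as Dose intensity/Planned dose intensity". The measure is summarised "with respect to an individual duration of treatment exposure as well as by cycle", as a continuous variable and in three bands: below 80%, 80% to 120%, and above 120%. SAP 7.2 describes the labels as "Phase I, where cohorts are defined by the dose assigned", and Protocol Appendix 1, footnote c, places cohort assignment before the first dose. The denominator is therefore fixed at the starting level.

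Elsewhere the SAP does follow the dose taken. Section 7.6 attributes each Phase I AE to the last dose before onset, and section 9.9.3 plots mean Phase I concentrations by the dose given before sampling. For efficacy, section 9.1 says: "The efficacy endpoints in phase I will be considered overall (i.e. all dose cohorts combined) and for the MTD cohort only". Section 9.6.2 speaks of summaries by cohort and overall.

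**The concern.** Relative dose intensity is read as a tolerability measure, and tolerability is the Phase I secondary objective. It should answer one question: how much of the dose intended for this patient was actually taken? Once a patient has been escalated as the protocol permits, the assigned-cohort dose is no longer the intended dose, and the ratio stops answering that question.

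Two things follow. A patient who does exactly as instructed can land in the band above 120%, beside any patient who took too much. And a patient who tolerates the higher level poorly and misses doses can land in the middle band, because the shortfall is offset by a denominator that is too small. The second is the more serious, since it flatters tolerability at the escalated level.

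**Working it through.** The plan states no relative dose intensity for an escalated patient, so there is no figure to reproduce. The check applies the SAP's definition to escalation paths.

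Inputs:
- Dosing is twice daily on each day of a 21-day cycle (Protocol 5.2.2), which is 42 doses per cycle.
- Phase I levels are 25, 50 and 75 mg BID (SAP 7.2; range in Protocol 5.2.2).
- The earliest escalation is after Cycle 1 (Protocol 3.1.4).
- Durations of 2 and 8 cycles are assumed for illustration; 8 is the cycle count used in Protocol 3.7.

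With assigned dose a, escalated dose b, e cycles at a, k cycles in all, full compliance and equal cycles:

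RDI = [a × e + b × (k − e)] / (a × k)

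Escalation straight after Cycle 1 (e = 1):

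| Path (mg BID) | 2 cycles | 8 cycles | Any escalated cycle alone |
|---|---|---|---|
| 25 to 50 | (25 + 50)/50 = 150% | (25 + 350)/200 = 187.5% | 50/25 = 200% |
| 50 to 75 | (50 + 75)/100 = 125% | (50 + 525)/400 = 143.8% | 75/50 = 150% |
| 25 to 75 | (25 + 75)/50 = 200% | (25 + 525)/200 = 275% | 75/25 = 300% |

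Later escalation gives smaller excesses. With escalation after Cycle 7 of 8, 25 to 50 gives (175 + 50)/200 = 112.5%, and 50 to 75 gives (350 + 75)/400 = 106.3%. Over all single-step paths of up to 8 cycles the range is about 106% to 275%, so some escalated patients stay within the 80% to 120% band.

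Masking. Take a patient assigned to 25 mg BID, escalated to 50 mg BID after Cycle 1, who takes half the doses in Cycles 2 to 8:
- Taken: 42 × 25 + 7 × 21 × 50 = 1,050 + 7,350 = 8,400 mg.
- Planned under SAP 9.7.1: 8 × 42 × 25 = 8,400 mg, so RDI = 100%.
- Prescribed: 42 × 25 + 7 × 42 × 50 = 1,050 + 14,700 = 15,750 mg, so the fraction taken is 8,400/15,750 = 53.3%.

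The patient belongs in the band below 80% but is reported in the middle of the 80% to 120% band. Reporting by cycle does not help: each affected cycle gives (21 × 50)/(42 × 25) = 100%, when half of the prescribed dose was taken.

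With the dose prescribed in each cycle as denominator, every fully compliant path gives 100%, and the half-dose patient gives 53.3% overall and 50% in each affected cycle.

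**The case against.** The strongest reply is that the effect may be small or absent. Protocol 3.1.4 caps escalation at the MTD and at levels the SAC has accepted. Protocol 1.3 reports 12 patients dosed, with DLTs at both 50 and 75 mg BID. The MTD is not stated, and the number escalated could be zero. This stands, and it is why the figures above are scenarios. In particular, a reader might infer that escalated patients will show 150% to 275%. The documents do not support that as a range: the upper end needs seven cycles at 75 mg BID after a 25 mg BID start, which the cap may bar, and other paths fall well below 150%.

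It can also be said that nothing is truly hidden. SAP 9.7.1 summarises cumulative dose and absolute dose intensity, tabulates interruptions and modifications with reasons, and lists all administration. This also stands: a careful reader of the listings would find the half-dose patient. It does not rescue the summary ratio, which would still be wrong for that patient overall and in every escalated cycle.

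A reader might go further and infer that Phase I efficacy is misattributed, or that the MTD-cohort result contains responses obtained above the MTD. The documents do not carry that. The cohort definition sits in a section on output labels, and analysis by assigned dose is a conventional choice for an exploratory, untested endpoint. The cap means that a patient assigned to the MTD has no permitted higher level. The only gap would be an escalation made before the MTD was known, to a level later judged too high, and nothing in the documents shows one.

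Dropping post-escalation responses would do harm. The first post-baseline scan falls around the end of Cycle 2 (SAP 6.1 under PFS; Protocol Appendix 1, footnote r). A patient escalated straight after Cycle 1 could then never count as a responder yet would stay in the denominator, which biases by-cohort ORR downward.

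**Conclusion.** The point holds for relative dose intensity and is minor. SAP 9.7.1 explicitly ties the denominator to the assigned cohort while the protocol permits the dose to rise, so any fully compliant escalated patient exceeds 100%, and the band above 120% cannot separate permitted escalation from over-dosing. Under-dosing after escalation can be masked, from 53% to 100% in the worked case.

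The sizes assume single-step escalation and equal cycles, with full compliance except in the masking case. How many patients are affected cannot be told from the documents. On efficacy there is no demonstrated error, only a useful item missing from the displays. DLTs are assessed in Cycle 1, before any escalation, and Phase II allows no increases, so neither primary analysis is touched.

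**What to change.** In SAP 9.7.1, for Phase I, define planned dose intensity from the dose level prescribed for each cycle, including escalations permitted under Protocol 3.1.4. State that reductions and holds for toxicity do not lower it, so that the ratio still registers poor tolerability. Use the same denominator for the whole-exposure summary, the by-cycle summary and the bands.

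For Phase I efficacy, keep the by-cohort tables by assigned dose, with post-escalation responses in the cohort numerator. Add the dose being taken at first response to the efficacy listings and the swimmers plot.

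The cost is a short SAP wording change and derived variables from dosing data already collected. It can be made before database lock, changes no clinical rule, and leaves the overall Phase I efficacy result as it is. If nobody was escalated, the tables do not change.

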### Summary of Protocol Changes

#### Inclusion/Exclusion Criteria

- The renal inclusion criteria is updated from  $\geq 60$  mL/min/1.73 m^2 to  $\geq 45$  mL/min/1.73 m^2.

In humans, elimination of AK-01 is anticipated to occur through oxidative metabolism followed by formation of glucuronide conjugates which are then excreted by the kidney. Conjugates such as these are typically pharmacologically inactive. Based on nonclinical data, approximately 15% of drug-related material was excreted in the urine, while the urinary elimination of intact AK-01 was less than 2%.

Since the contribution of renal elimination is predicted to be minimal, diminished renal function should not significantly affect overall AK-01 exposure.

Furthermore, the toxicity profile of AK-01 is monitorable and reversible. Dose escalations will be guided by safety, exposure, and PD data (as available) and will only be allowed after careful examination of the tolerability data of the dose in the previous cohort.

~~In humans, excretion of AK-01 is anticipated to occur through metabolism followed by renal excretion, based on dog and monkey data that indicate that the urinary excretion of AK-01~~

is likely to be insignificant (less than 2%). In addition, F-NMR data indicated that the amount of drug-related material excreted from urine was 15% of dose after oral dosing. Slow clearance was determined in preclinical species (5.5-37% of hepatic blood flow) with bile excretion and metabolism as the major clearance pathways. Acyl glucuronidation and oxidative metabolism were major metabolism pathways. Glutathione conjugates were found in rodent hepatocytes, rat bile and urine and monkey feces, but not in human liver hepatocytes. No metabolites were observed in incubations with human recombinant P450s (rCYPs) and human liver microsome CYP fingerprinting assays, thus, the CYP isoform(s) responsible for LSN3295668 metabolism could not be identified.

Since the contribution of urinary excretion to the metabolism and excretion of AK-01 is predicted to be minimal, a diminished renal function should not significantly affect overall exposure.

Furthermore, the toxicity profile of AK-01 is monitorable and reversible. Dose escalations will be guided by safety, exposure, and PD data (as available) and will only be allowed after careful examination of the tolerability data of the dose in the previous cohort.

### **Protocol Version 4: AURA-001(c), 10/Apr/2018**

Protocol AURA-001 [A Phase I/II Open-Label Multicenter Study to Evaluate the Safety and Efficacy of AK-01 as Monotherapy in Patients with Locally Advanced or Metastatic Solid Tumors] has been amended to create Version 4, dated 10/Apr/2018. The new protocol is indicated by amendment (c) and will be used to conduct the study in place of any preceding version of the protocol.

The overall changes and rationale for the changes made to this protocol are as follows:

- Data from the ongoing Phase I added
- A 25 mg BID was selected as the Phase II dose. This has been added as appropriate.
- Phase II population has been revised as below and included at all relevant places in the protocol:
  - Initially patients with SCLC and HER-2 negative BC will be enrolled in 2 cohorts. Subsequently, at sponsor's discretion, patients with following tumor types may be enrolled in additional 2 cohorts: triple negative breast cancer, squamous cell cancers of the head neck that are HPV+ and have failed standard therapy, and/or any other tumor type that warrants further exploration.
- Additional information were added to the inclusion criteria for all cancer/tumor types.
- Sample size of Phase II was revised from 80 patients to 120 patients overall ( $\leq 30$  patients in each of 4 cohorts).
- A clarification added that all study sites will use the same formula for calculation of eGFR.

## Revised Protocol Sections

**Note:** Deletions have been identified by ~~strikethroughs~~ or grayed out for figures. Additions have been identified by the use of underscore.

### 1.2. Rationale and Justification for the Study

Preclinical data demonstrating biologic activity *in vivo* with an acceptable safety profile supports the evaluation of AK-01 in humans.

The selectivity of AK-01 for AurA differentiates AK-01 from other inhibitors of Aurora kinases (e.g., MLN8237, AZD1152, and PHA-739358), and may allow AK-01 to elicit the benefits of AurA inhibition without triggering the adverse and often dose-limiting neutropenia associated with AurB inhibition.

The present study will evaluate the safety and efficacy of AK-01 in patients with locally advanced or metastatic solid tumors, with an emphasis on small-cell lung cancer (SCLC), estrogen receptor (ER+) and/or progesterone receptor (PR+) positive/HER2-negative breast cancer (BC), triple negative- breast cancer (TNBC), human papilloma virus (HPV) associated squamous cell cancers of the head neck, and any other indication that warrants further exploration. A large proportion of ~~SCLC and hormone-positive BC~~ these patients bear a *Rb1* loss-of function mutation, a molecular signature which sensitized animal models to AK-01 in preclinical testing (see Investigator's Brochure). Patients are eligible for the Phase II part of this study if they have failed standard of care therapies which do not preclude therapy with an AurA inhibitor: hormone therapy and CDK4/6 inhibitor for ER+ and/or PR+ BC, and platinum-based- therapy for SCLC, relapsed/resistant TNBC, HPV associated squamous cell cancers of the head neck, and any other indication that warrants further exploration (see Investigator's Brochure for further details).

### 1.3. Data from Ongoing Phase I Part of the Study

A total of 11 patients have been dosed in the ongoing Phase I part of the study since June 2017 with doses of AK01 of up to 75 mg BID. Dose limiting toxicities (DLTs) were noted at both 75 mg and 50 mg dose levels. The 25 mg twice a day (BID) dose has been chosen as the dose for Phase II.

Based on safety analysis of the ongoing Phase I part of the study, the following are considered as potential adverse events (AEs): bone marrow toxicity including neutropenia and thrombocytopenia; gastrointestinal toxicity including mucositis and diarrhea; and corneal deposition with blurry vision and double vision. Appropriate follow up and rapid therapy for any of these events will be undertaken.

Additional information on the reported AEs is available in the investigator's brochure (IB).

## 2 STUDY OBJECTIVES

### 2.1 Phase I

The exploratory objectives are:

- To evaluate the pharmacokinetic (PK) and pharmacodynamic (PD) characteristics of AK-01.
- To compare PD markers of AK-01 target engagement in ~~skin and~~ tumor biopsies.
- To assess preliminary evidence of AK-01 anti-tumor activity.

[figure not shown]
## 3. INVESTIGATIONAL PLAN

This open-label, non-randomized, multi-center study will explore the safety, PK, PD, and efficacy of AK-01 administered in 21-day cycles to patients with locally advanced or metastatic solid tumors.

In Phase I of this study, patients with locally advanced or metastatic solid tumors (all-comers) will be administered AK-01 according to a multiple ascending dose (MAD) schedule to determine the MTD. The phase II dose (P2D) may be confirmed in up to 6 additional patients, and may take into consideration the MTD, evidence of AurA and AurB target engagement, and PK. The P2D will not exceed the MTD. Throughout Phase I, safety, tolerability, PK, PD, and early evidence of anti-tumor activity will be assessed.

[figure not shown]
In Phase II of this study, AK-01 will be administered in up to ~~34~~ cohorts: initially in patients with SCLC and BC, and subsequently, at the sponsor's discretion, in patients with one of the following: TNBC, HPV associated SCC-HN, and/or any OT that warrants further exploration. ~~BC, SCLC, and/or one other solid tumor type. Specific inclusion/exclusion criteria to support a third tumor type will be added to the protocol by amendment.~~ Efficacy, safety, PK, and PD will be assessed.

An overview of the study design is given in Figure 1.

Notes: Dose escalation in Phase I will follow a 3 + 3 design; dosing may vary from proposed doses for safety reasons. Following identification of the MTD, the P2D may be explored in up to 2 additional cohorts. Phase II will consist of up to 3 cohorts: SCLC, BC, and/or one other solid tumor of interest.

Abbreviations: BC – breast cancer; BID – twice daily; MTD – Maximum Tolerated Dose; P2D – phase II dose; SCLC – small-cell lung cancer; TBD – To be determined

Notes: Dose escalation in Phase I will follow a 3 + 3 design; dosing may vary from proposed doses for safety reasons. Following identification of the MTD, the P2D may be explored in up to 2 additional cohorts. Phase II will consist of up to 4 cohorts of patients with locally advanced or metastatic 1) BC; 2) SCLC; 3) TNBC; 4) HPV associated SCC-HN; and/or 5) OT that warrants further exploration.

Abbreviations: BC – breast cancer; BID – twice daily; HPV – human papilloma virus; MTD – Maximum Tolerated Dose; OT – other tumor type; P2D – phase II dose; SCC-HN – squamous cell cancers of the head neck; SCLC – small-cell lung cancer; TNBC – triple negative breast cancer

